During the screening or baseline study visit, all participants will receive training to appropriately check blood pressure at home using study-issued home blood pressure monitors. A baseline chemistry panel and assessment of albuminuria will be ordered, if not completed clinically within 3 months of the study visit.

Both groups will complete an initial study visit with the study team and physician and complete a 24-hour ABPM session. The ABPM session can be done prior to training for the intervention participants.

4. Random allocation and blinding. Randomization will be 1:1 intervention/control. Randomization will be done by a central system, stratified by degree of hypertension at initial visit (> 160 systolic or below) and block-randomized by clinical sites using the centralized randomization tool through the Health Services Research Center data servers. The study participants and personnel will be unblinded. The research assistant in charge of checking blood pressures at the initial, 6-month, and 12-month visits may be aware of treatment allocation but will use standard procedures and an automated Omron cuff, using the SPRINT study blood pressure measurement protocol (5 minutes of quiet rest followed by 3 automated blood pressures at one-minute intervals, averaging last 2 to determine in-clinic BP), to ascertain blood pressures to avoid digit preference and bias.

5. Follow-up study visits: Participants in both randomization arms will then return for 6-month and 12-month study visits at which times blood pressure will be checked by a research assistant, and participants will complete questionnaires similar to those obtained at baseline, blood and urine studies for kidney function and albuminuria (as part of routine clinical care) at 12-month visit, and repeat ABPM at both 6 and 12-month visits.

6. Usual care and intervention protocols. Both groups will be issued a home blood pressure cuff with data recording capabilities identical to that in the active arm of the study, (Microlife BP, Microlife USA Inc), will meet the study physician and have questions answered, and will be instructed to record and share results with their primary care physician at routine clinic visits. The patient's and provider's willingness to titrate to a clinical goal of 130/80 (home goal of 120/75) will be confirmed.

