Usual care: For those in the **usual care group**, further hypertension care and laboratory monitoring will be assumed by the primary care physician at intervals chosen by that physician in terms of frequency of follow-up or testing, and patients in this study arm can be referred for any support plan that is part of usual care, including nurse visits, home telehealth, or pharmacist visits. Participants will return to the study visit at month 6 and 12 to complete the same study measures summarized above including ABPM measures. Blood pressure will be recorded at these visits but medication changes will not be part of these visits so as not to affect blood pressure treatment in the usual care group. We will track medication changes in the usual care group via chart review.

Intervention: The **intervention group** will be issued a home blood pressure cuff with data recording capabilities, identical to that in the control group, and instructed in its use. As part of the initial study visit with the study physician and study nurse they will learn about and review the blood pressure action algorithm (**see Figure**) and its use. Goal blood pressures in the home action algorithm are lower than in-clinic targets; it has been consistently demonstrated that home SBP is on average 10 mm Hg lower than in-clinic BP in most patients, so if the primary care clinician's stated target for a given patient is 130/80, the home target corresponding to this is 120/75.

The patients in the intervention group are provided with extensive training on how to write down their blood pressure readings, when to initiate a change, and how to track their medications using a Participant Training Standard Operation Procedure (attached in Appendix.) They are instructed to call their PCP with side effect issues, as would be done for normal medication changes. They are further instructed to call with issues related to self-monitored low or high blood pressure, per the color-coded charts provided. A training reinforcement call will also be made by the study coordinator to each of the participants in the intervention group after the training visit to ensure that each participant is fully confident in carrying out all aspects of the study.

Patient handouts and assessments:

- 1. Training Exercises
- 2. Patient Training Notes
- 3. Action Sheet
- 4. Contact Information Sheet
- 5. Weekly Reading Logs
- 6. Medication Change Details Forms
- 7. Color Coding Chart for patients

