The primary care team will be able to stop, start, or alter the doses of medications based on new clinical information. All study-related prescription fills and use of antihypertensive medications outside the scope of the study will be tracked. Some safety issues will be monitored in this fashion as well: If a patient (for example) attempts to activate 2 steps in the course of a week (which would violate the monitoring protocol, which specifies a longer interval of home monitoring prior to a new medication) that will be considered a potential safety violation related to the self-management protocol. We note that we cannot capture via pharmacy records all instances of medication mismanagement or non-compliance by patients either in the selfmanagement or the usual care arm.

Follow-up laboratory testing for electrolyte abnormalities (basic chemistry panel) will be triggered by any request by a patient for Step 3 or Step 4 medications. The initial instruction manual for self-management will clearly indicate that laboratory tests must be done after adding a medication with electrolyte effects. Participants will be reminded of the need for laboratory testing by specific labeling on the new medication bottle. Those who do not report for the required laboratory test within a two week window will receive a phone call from study staff reminding them to do so. These laboratory studies will be routed primarily to the study team, with additional mandatory notification to the primary care team; **any action on abnormal labs will be primarily managed by primary care, with oversight by study physicians to ensure safety**. Between-visit contact with the study will be limited to patient-triggered calls to issue blood pressure medication according to the algorithm. All other care will be handled by the primary care team. Patients who require all 4 steps of the algorithm and are not at blood

pressure target will be considered to have exhausted the self-management algorithm and will then be treated at the discretion of their primary care physician. Follow up will continue by protocol to allow analysis of data by intent-to-treat.

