At the baseline, six-month, and twelve-month visits, the blood pressure will be measured by a research protocol (3 measurements with interval pauses as above). The blood pressure from the research study visit on the day of randomization will serve as the baseline study visit for this trial. The outcome blood pressure will be the similarly measured (research protocol) blood pressure at the 12 month study visit.

ABPM set-up will be done according to our previously used Spacelabs protocols from SPRINT study.

All study instruments will be administered by research staff in-person with patients at the baseline, 6 and 12 month visits.

Chapter 8. Safety Monitoring and Reporting

The main clinical adverse events that will be monitored during this trial are those related to overor under-treatment of blood pressure. These were not different from usual care during the two studies of similar interventions in the UK, and only 3% of those in the intervention group deviated from self-titration protocols in those studies. Nevertheless, we plan to actively monitor for these issues by scheduled chart review for clinical or ER visits, hospitalizations, and potentially study-related serious adverse events (e.g. syncope, hypertensive urgency, stroke, MI, death). Other adverse events potentially related to the study will also be collected (e.g. medication side effects, abnormal laboratory findings including sodium < 130 or potassium <3 (for those on thiazide); potassium >6 for those on ACE; creatinine 50% higher than baseline).

We have assembled a DSMB for this study given the potential risks of self-management of blood pressure. This will consist of experienced nephrologist-epidemiologists and a general internist, all working in the VA system. Assisted by the study statistician they will review AEs and BP data in both groups at the point where each group of 100 participants have reached the six-month time point.

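### Between baseline and month 12 only the self-management arm has protocol-driven chemistry panels, and some laboratory limits depend on drug, so an arm difference in laboratory adverse events cannot be read as a treatment effect

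*Combined protocol and SAP*

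**What the plan says.** **Interim testing.** Chapter 2, section 6 states that follow-up chemistry testing "will be triggered by any request by a patient for Step 3 or Step 4 medications". The test is enforced: "Those who do not report for the required laboratory test within a two week window will receive a phone call from study staff". Only self-managing participants can make such a request. For usual care, the same section says that "further hypertension care and laboratory monitoring will be assumed by the primary care physician at intervals chosen by that physician".

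**Testing common to both arms.** Chapter 2, section 3 covers baseline: "A baseline chemistry panel and assessment of albuminuria will be ordered, if not completed clinically within 3 months of the study visit". Section 5 adds, for both arms, "blood and urine studies for kidney function and albuminuria (as part of routine clinical care) at 12-month visit". The measures tables (Chapter 2 and section 4.3) mark the chemistry panel at screening and at 12 months, and as needed in between.

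**What counts as an event.** Chapter 8 gives as examples of laboratory adverse events "sodium < 130 or potassium <3 (for those on thiazide); potassium >6 for those on ACE; creatinine 50% higher than baseline". Section 4.3 shows that default Step 3 adds a thiazide and an ACE inhibitor in one combination pill, and that Step 4 raises the dose of both.

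**Who looks at the counts.** Chapter 8 says of the DSMB that "they will review AEs and BP data in both groups" as each 100 participants reach six months. Chapter 2, section 8 describes the same review as covering SAEs and in-clinic blood pressure.

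**The concern.** A laboratory abnormality without symptoms is found only if blood is drawn. From baseline to month 12 the protocol draws blood in one arm, at the moment when new drugs are added, and leaves the other arm to clinical habit. Drug-conditional limits add a second asymmetry. A potassium value that meets the limit is named as an event in a participant on the relevant drug, but not in a participant on another drug.

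Nothing in the plan adjusts for this. No count of panels per arm is planned, step-triggered findings are not separated out, and the panel that both arms share is not named as the basis for comparison.

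What is at stake is the reading of safety. The stated expectation is that safety will be similar in the two arms, and the DSMB may halt the trial for SAEs or other concerns. An imbalance in laboratory events could be taken as harm from self-management when it partly shows more testing. Abnormalities in usual care could equally go uncounted.

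**Working it through.** **1. Post-baseline chemistry testing, by arm**

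| Period | Self-management | Usual care |
|---|---|---|
| Baseline | Panel | Panel |
| Between baseline and month 12 | Panel at each Step 3 or 4 request, with reminder call; otherwise as needed | As the physician chooses |
| Month 12 | Panel, as routine care | Panel, as routine care |

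The arms differ by design only in the middle row. The DSMB looks fall there: they are timed at 100, 200 and 300 participants reaching six months, and participants who have only just reached six months do not yet have the shared 12-month panel.

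**2. The limits.** Potassium below 3 is tied to thiazide use and potassium above 6 to ACE inhibitor use. The sodium limit may or may not be covered by the thiazide condition, because the wording is ambiguous. The creatinine criterion has no drug condition. No criterion is restricted by arm.

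**3. Where the counts are used.** Hypothesis 2 (Chapter 9, section 2) applies Fisher's exact test to medication-related SAEs, unscheduled visits, patient-reported symptoms, ER visits and hospitalizations. Non-serious laboratory events are not on that list. They enter the DSMB review as Chapter 8 describes it, and any adverse event tables.

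**4. The plan's own figure.** The only design calculation is for systolic pressure: n per arm = 2 × (1.960 + 0.842)² × 16² / 5² ≈ 161, and 161 / 0.80 gives 202, against the stated 200. Power with 160 completers per arm is 79.8%, against the stated 80%. It reproduces, but it does not bear on this point. The documents give no laboratory event rate and no testing rate.

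**5. Illustration; every input except the 200 per arm is assumed.** Let
- r = true incidence of a laboratory abnormality over the year, equal in both arms (3% to 10%);
- f = share of the self-management arm reaching Step 3 or 4 (20% to 60%), in whom an abnormality is always found;
- s = probability that an abnormality is found in everyone else (30% to 70%).

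The observed rates are r × [f + (1 − f)s] under self-management and r × s under usual care. The rate ratio is [f + (1 − f)s] / s.

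With r = 5% and 200 per arm:

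| f | s | Rate ratio | Expected events, self-management vs usual care | Fisher rejects (two-sided 0.05) |
|---|---|---|---|---|
| 20% | 70% | 0.76 / 0.70 = 1.09 | 7.6 vs 7.0 | 2.7% |
| 40% | 50% | 0.70 / 0.50 = 1.40 | 7.0 vs 5.0 | 4.6% |
| 60% | 30% | 0.72 / 0.30 = 2.40 | 7.2 vs 3.0 | 16.1% |
| any | 100% | 1.00 | 10.0 vs 10.0 | 2.9% |

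Over the whole grid with s from 30% to 70%, the rejection rate runs from 1.1% to 40.0%. With equal detection (s = 100%) it is 2.2%, 2.9% and 3.4% for r = 3%, 5% and 10%. The Fisher column only gives a sense of scale, since no such test of laboratory events is planned.

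The first DSMB look has about 50 participants per arm. Using the same inputs, expected counts run from 50 × 0.05 × 0.76 = 1.9 vs 50 × 0.05 × 0.70 = 1.75, to 50 × 0.05 × 0.72 = 1.8 vs 50 × 0.05 × 0.30 = 0.75. Chance can easily hide or exaggerate differences of that size.

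The illustration leaves out any real drug effect and does not model the drug-conditional limits.

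**The case against.** The case on the other side is substantial, and most of it narrows the point.

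- **Both arms are tested by protocol.** A reader might infer that laboratory events are looked for only in the self-management arm. Over the whole study that is wrong, because both arms have baseline and 12-month panels. It holds only for protocol-driven testing in between.
- **An excess is not assured.** A reader might infer that the safety review is bound to show one from detection alone. The documents do not support this. Chapter 8 notes that these tests are used in routine care, so usual-care physicians may test often, and the ratio is 1.00 if their detection is complete. Part of any excess could also be a real effect of added thiazide or ACE inhibitor exposure.
- **The drug conditions do not simply favor one arm.** They apply in both. Self-management participants already on one drug are by default switched to amlodipine, while usual-care participants may stay on a thiazide or ACE inhibitor. Which arm has more qualifying participants before Step 3 is not established. The list in Chapter 8 is also open-ended, so other abnormalities are not excluded.
- **Hypothesis 2 does not test non-serious laboratory events.** The formal tests are touched only if an abnormality found on a triggered panel leads to a visit or an SAE.
- **The DSMB is unblinded and expert.** It can know which arm has triggered panels, and no halting threshold rests on laboratory counts.
- **The 12-month panel is not a full answer.** It cannot serve six-month looks, and early action on abnormal results could lower self-management counts at month 12.

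All of these stand as limits on the claim. They do not remove the unequal interim testing or the drug-conditional limits, and the plan offers nothing to separate detection from risk. A DSMB that is not shown panel counts cannot make the correction itself.

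**Conclusion.** The concern holds in limited form. Between baseline and month 12, protocol-driven chemistry testing occurs only under self-management, and the potassium limits (arguably the sodium limit too) are conditional on drugs that default Steps 3 and 4 add. An arm difference in laboratory adverse events, at a DSMB look or in the final tables, may therefore reflect unequal detection and cannot be read as a treatment effect.

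The direction from testing alone is toward more events under self-management if usual care tests less completely. The size cannot be derived from the documents: the range of 1.09 to 2.40 rests wholly on assumed values of f and s. The primary outcome is untouched. This is a cheap improvement to interpretation and does not show that a planned test is invalid.

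**What to change.** Keep all safety testing as it is. In Chapters 8 and 9, for between-arm tabulation:

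1. Apply the sodium, potassium and creatinine limits to every participant, whatever drug they take.
2. At each DSMB look and in the final report, show the number of participants tested and the number of panels done in each arm. List abnormalities from step-triggered panels separately, as safety monitoring of the intervention arm and not as a comparison.
3. Base the final between-arm laboratory comparison on the 12-month panel against baseline, which both arms have. Do not use it as the basis for the six-month DSMB looks.
4. Reconcile Chapter 2, section 8 (DSMB reviews SAEs) with Chapter 8 (DSMB reviews AEs).

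The cost is some wording and a few table rows; no new tests are needed. The downside is that the 12-month comparison misses transient abnormalities and may understate intervention-arm events that were found and acted on earlier. Those found on step-triggered panels stay visible in the separate listing.

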Centers also need to keep a listing of why the participant who was told about the study decided not to participate. These reasons are recorded on "The Reasons Why Participants who are Approached and do not Consent" tally sheet. This evaluation of reasons for non-enrollment and chart-based outcomes of non-enrollees is key to planning for dissemination of this technique within diverse VA sites and populations.

Criteria for exclusion will include:

- Active prescriptions for > 1 antihypertensive agent (excluding chronic agents prescribed primarily for other purposes, such as alpha blockers for prostate disease or PTSD);
- Known allergies to 2 or more antihypertensive agents;
- Specific reasons for a blood pressure target different from in-clinic target of 130/80, or a corresponding home management goal of 120/80
- Currently not primarily in charge of his/her own medication administration (e.g. those living in institutions or with dementia or other limitations making self-medication care not possible);
- Life expectancy of < 12 months;
- Blood pressure at screening visit > 180 mm Hg systolic or > 110 diastolic, or < 130 systolic; screening cognitive function (Montreal Assessment of Cognitive Function, MoCA)⁵⁰ score less than 25;
- eGFR < 25 ml/min /1.73m² or end-stage renal disease (ESRD);
- Inability to use a standard home blood pressure cuff;
- Known secondary cause of hypertension that causes concern regarding safety of the protocol, in the opinion of the site investigator;
- Cardiovascular event or hospitalization for unstable angina within last 3 months;

- Symptomatic heart failure within the past 6 months or left ventricular ejection fraction < 35%;
- Pregnancy or planned pregnancy, or of child-bearing age not using birth control;
- Current participation in another clinical trial;
- Major factors judged to be likely to significantly limit comprehension of or adherence to interventions including dementia, psychiatric disease, or substance abuse.
- Cancer treatment within the last year

Primary care physicians and study staff will be able to exclude participants based on their judgment of the patient's capability to undergo the intervention.

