8. Safety metrics. We will assess SAEs both by active chart surveillance for ER or unscheduled clinic visits for enrolled veterans as well as by interview at the study visits. The CPRS system allows automated notifications to study physicians and staff for all patients enrolled in the study, so that admissions and ER visits can be reviewed on an ongoing basis; we will compile these quarterly. Every time a new medication is requested, a chart review by study staff will be triggered to confirm that medications are not being requested too frequently (protocol violation) in the intervention arm. Participants with significant safety violations in the intervention arm, identified either through interval contact or through log reviews at the 6 month visit, will be considered to have failed self-management and will be returned to usual care. Participant-reported side effects and adverse events will be actively collected at the 6-and 12-month visits in both groups.

Potentially study-related SAEs and all hospitalizations and major events will be reviewed locally by the study physicians. An un-blinded DSMB consisting of 3 experienced nephrologist-epidemiologists and a general internist, all working in the VA system and assisted by the study statistician, will review SAEs and in clinic BP data in both groups at the point where 100

participants reach the six-month time point, and every time an additional 100 participants reach six months. Any major interval SAEs or concerns will be communicated to the lead member of the DSMB who will have the option to ask for a full review.

9. Patient oriented metrics.

The Patient-Practitioner Orientation Scale has been used in prior hypertension studies at VA and assesses patients' preferred role orientation (patient- vs. provider-centered) in their clinical encounters.

Acceptability: Acceptability of the intervention will be measured using research study retention rates, patient satisfaction questionnaires including both quantitative and qualitative ratings, and adherence measures described below. We will assess participant satisfaction using 10 questions developed by the investigators. Similar questions have been used by [name] in other studies. (See Appendix 1). Clinicians with at least 2 intervention participants in the study will be surveyed with two simple Likert-scale questions regarding their opinion of the intervention and whether they would want future patients to use a similar plan.

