Adherence: Adherence to the intervention protocol will be measured using data on patterns of use of the home blood pressure cuff in comparison with the recommended schedule of monitoring, and self-reported and pharmacy-confirmed medication requests in response to blood pressure results. We will issue medications for all participants enrolled in this study as 30-day refills, to best estimate medication possession ratios over the 12 month study. The Morisky medication adherence scale will be used to assess participants' medication adherence behavior at each study visit.

Self-efficacy: Self-efficacy for hypertension self-care reflects levels of confidence in the ability to perform basic self-care activities crucial to the intervention as well as confidence that these activities can be performed and be beneficial as a whole. The wording of the items has been adapted to be specific to hypertension self-care (see Appendix). The measure consists of 6 items, rated on a 10-point scale.

Health-related quality of life (HRQOL): We will administer the EQ5D questionnaires to assess HRQOL at baseline, to assess the impact of baseline health status in this population.

Chapter 3. Recruitment and Informed Consent

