 Primary care 'burnout' from study burdens – confusion about response to participants in a blood pressure study

Approach: repeated and patient education, for both physicians and PACT team

Chapter 6. Procedures for Inactive/Lost/Refused Participants and Missed Visits

During the course of the study, we may find that certain participants become disinterested or frustrated. Participants in the active arm of the study may fail that arm (because of increasing meds above study titration plan, failure to follow protocol, etc) but should stay in the study for follow up purposes in intention to treat fashion.

Potential status options for a participant are:

- Active status a participant is considered to be active if following the assigned randomized treatment and in contact with the study.
- Inactive status a participant is considered to be inactive if he or she is no longer selfmonitoring/self-managing for any reason (but is still in contact with study).
- Lost status a participant is considered to be lost-to-follow-up if he/she has
 missed more than a follow-up visit, cannot be contacted by any ordinary
 means (e.g., home phone, cell phone, mail, email, fax, etc.), clinic staff do not know the
 participant's whereabouts, and alternative contacts either do not know where the
 participant is or cannot be contacted themselves.
- Refused status a participant is considered to be refused if he/she has withdrawn consent to participate in the study and refuses further contact for any reason.

To the greatest extent possible, we will attempt to complete follow-up visits for participants who are either active or inactive and to contact lost participants.

Chapter 7. Ascertainment of Study Outcomes

Blood pressure will be measured in the primary care clinic at the start of the study. We will use the clinically measured blood pressure as the blood pressure used for eligibility criteria, since primary care physicians may act on this blood pressure prior to the patient enrolling in the study.

Study clinic blood pressure will also be used to verify primary care clinic measurements and ensure that blood pressure is at least 130 systolic at baseline.

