Hypothesis 3: End-of-study levels of acceptability of the self-management protocol will be high. Patient self-efficacy will be higher in the self-management arm relative to the usual care arm. End-of-study acceptability scores will be reported descriptively as percentages. For self-efficacy scores and other scores measured at multiple time points, the change in outcome from baseline to month 12 will be compared between two study groups, and we will use similar analysis methods as those used for Hypothesis 1a.

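### Study retention cannot show whether participants accepted self-management, because those who stop are kept in follow-up by design; persistence with self-management should be reported for Hypothesis 3 instead

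*Combined protocol and SAP*

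**What the plan says.** Chapter 2, section 9 gives three patient-level measures: "Acceptability of the intervention will be measured using research study retention rates", then "patient satisfaction questionnaires including both quantitative and qualitative ratings, and adherence measures described below". The adherence paragraph that follows begins "Adherence to the intervention protocol will be measured using data on patterns of use of the home blood pressure cuff" and adds medication requests. There is also a short clinician survey: "Clinicians with at least 2 intervention participants in the study will be surveyed".

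On people who leave self-management, Chapter 6 says that those who fail the active arm "should stay in the study for follow up purposes in intention to treat fashion". It defines a separate status for them: "a participant is considered to be inactive if he or she is no longer selfmonitoring/self-managing for any reason", provided contact continues. Lost and refused are further statuses. Chapter 2, section 6 and section 4.3 likewise keep in follow-up those who cannot be trained, those uncomfortable after two sessions and those withdrawn by the investigator. Chapter 5 ties the financial incentive to completing the 6- and 12-month visits.

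Hypothesis 3 (Chapter 9) predicts that acceptability of the self-management protocol will be high. Its analysis is one sentence: "End-of-study acceptability scores will be reported descriptively as percentages". No threshold, denominator or rule specific to missing scores is given.

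**The concern.** Hypothesis 3 is about the self-management protocol, whereas retention is about the study. The plan separates the two on purpose: someone may abandon self-management in month 1, attend both visits and count as retained. Keeping such people is right for the blood pressure analysis, but it makes retention uninformative about whether they accepted the intervention.

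End-of-study scores have a different gap. Chapter 7 has the instruments administered in person at visits, so lost and refused participants give no month-12 score, and the general missing-data text in Chapter 9 allows deletion. A reader deciding whether to spread self-management within the VA could be shown a retention figure and a respondents-only percentage, without learning how many of those assigned to self-manage were still doing so.

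**Working it through.** **1. The plan's own figures.** Inputs (Chapter 9, sample size and power): difference 5 mm Hg, SD 16, two-sided 0.05, 80% power, attrition 20%; 1:1 allocation (Chapter 2, section 4). Completers per arm = 2 × (1.960 + 0.842)² × 16² / 5² = 160.8, rounded up to 161. Dividing by 0.80 gives 202 per arm, or 404. The plan states 400 recruited and 320 completing; 160 per arm gives 79.8% power. The figures reproduce and are not disputed. They supply the 200 randomized and 160 attending used below.

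**2. Retention against persistence.** Retention is taken as month-12 attendance, since the plan does not define the rate. Let *a* be attrition and *s* the share of the arm who stopped self-managing but attend month 12.

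- Retention = 1 − *a*
- Known to be still self-managing = 1 − *a* − *s*
- Difference = *s*, whatever the attrition

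With *a* = 20% and an assumed range for *s*:

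| *s* | Retention | Still self-managing |
|---|---|---|
| 0% | 160/200 = 80% | 160/200 = 80% |
| 3% | 80% | 154/200 = 77% |
| 10% | 80% | 140/200 = 70% |
| 20% | 80% | 120/200 = 60% |
| 30% | 80% | 100/200 = 50% |

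The values of *s* are assumptions. The constant middle column follows from the design.

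**3. Whether adherence closes the gap.** Only partly.

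- Cuff memory is downloaded at the 6- and 12-month visits (Chapter 9, data analytic plan), so non-attenders have gaps.
- Both arms receive the same cuff and are told to record readings (Chapter 2, section 6), so cuff use does not by itself prove self-management.
- Few medication requests may mean controlled pressure or disengagement.
- Chapter 2, section 6 concedes that pharmacy records miss some non-compliance.
- Hypothesis 3 does not say how adherence enters its conclusion.

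**4. End-of-study scores.** Suppose 90% of the 160 attenders are satisfied (assumed): 144. Over all 200, the figure is 0.80 × 90% + 0.20 × *g*, where *g* is the share of non-attenders who would be satisfied. For *g* = 0%, 25% and 50% this gives 72%, 77% and 82%. The 72% is a worst case.

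Attending stoppers pull the score the other way. With 20% of the arm stopped, 90% satisfaction among the 120 still active and 40% among the 40 stoppers (assumed), the attenders' score is (108 + 16)/160 = 77.5%. Follow-up of stoppers therefore lets the score reflect their views.

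**5. Clinician survey.** Patients per clinician are not given. If 200 intervention patients fall at random over 50, 100, 150 or 200 clinicians (assumed), then 7%, 31%, 48% or 58% of clinicians with any such patient have exactly one and are not asked.

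Whether that biases the result depends on who they are. Take half of clinicians as favourable, with Poisson patient counts. If favourable and unfavourable clinicians both average 2 patients, the share favourable is 50% under either an at-least-2 or an at-least-1 rule. If they average 2 and 1 respectively, it is 69% under at-least-2 and 58% under at-least-1.

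**The case against.** The strongest reply is that retention is only one of three patient-level measures. Adherence is named in the same sentence and would expose many who attend but have stopped. Stoppers are also kept for visits, and nothing excludes them from the survey. The measures table in section 4.3 marks the Program Evaluation Survey at 6 months as well as 12, so some later losses will already have given ratings. Training failures must have a reason recorded, and status categories exist. All of this stands. A reader might infer that every acceptability measure loses the people who rejected the intervention; the documents do not support that.

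A reader might also infer that unfavourable clinicians escape the survey by keeping their patients out, since "Primary care physicians and study staff will be able to exclude participants based on their judgment". That sentence goes on to tie the judgement to the patient's capability for the intervention. Allocation is central and 1:1, so many clinicians will have 0 or 1 intervention patient by chance, and those with none have no experience to rate. Selection of favourable clinicians is possible but not shown.

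Finally, simply substituting active status for retention would mislead. Inactive status covers any reason, so it could include participants who used all four steps and then passed to primary care (Chapter 2, section 6), and those withdrawn for safety. Neither is a refusal. This objection is sound and shapes the fix.

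**Conclusion.** The point holds for retention. As a measure of acceptability it exceeds persistence by the proportion who stopped self-managing but still attend: 3 to 30 percentage points over the assumed range, and zero if nobody stops. Because some stopping is not the participant's choice, that proportion is an upper limit on the overstatement of acceptability itself. Adherence data reduce the blind spot without removing it, and month-12 scores lack lost and refused participants.

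It would go too far to say that Hypothesis 3 is biased toward a high result. Its analysis names only scores and does not say how retention or the clinician survey feeds the conclusion, so overstatement is a risk, not an established effect. The acceptability part is descriptive and secondary, and the primary blood pressure analysis is unaffected. The case for acting is that a better measure is available from statuses the plan already defines.

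**What to change.** In Chapter 2, section 9 and under Hypothesis 3:

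- **Persistence.** Make the acceptability measure the proportion still self-managing at month 12 among all randomized to that arm, using the Chapter 6 statuses. Show study retention separately.
- **Reasons.** Break non-active participants down by training failure, participant choice, investigator or safety withdrawal, lost, and refused. Show those who completed all four steps and passed to primary care as a separate category, not counted as non-acceptance.
- **Satisfaction.** Report it among respondents, with the number of respondents out of all randomized to the arm. Add a bound that counts non-respondents as not satisfied, labelled as the worst case.
- **Clinicians (optional).** Send the two questions to every clinician with at least one intervention participant.

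The cost is wording and a little tabulation. The statuses are already defined. The documents expressly require a recorded reason only for training failures, so a reason code for later stops should be confirmed or added. The acceptability figure may look slightly less favourable. The optional step adds some two-question surveys.
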